10.3.4. Reporting of SAEs

SAE Reporting via Paper CRF

- Facsimile transmission of the SAE paper CRF is the preferred method to transmit this information to the sponsor or designee.
- Initial notification via telephone does not replace the need for the investigator to complete and sign the SAE CRF pages within the designated reporting time frames.
- Contacts for SAE reporting can be found in the SAE Report.

10.4. Appendix 4: Liver Safety: Suggested Actions and Follow-up Assessments

At the PI's discretion, in the event of suspected hepatic impairment of a study participant, close or comprehensive monitoring may be conducted.

Close hepatic monitoring

Laboratory tests (Appendix 2, Section 10.2), including ALT, AST, ALP, TBL, as well as direct bilirubin, gamma glutamyltransferase, and creatine kinase, should be conducted.

These should be repeated within 48 to 72 hours to confirm the abnormality and to determine if it is increasing or decreasing, if 1 or more of these conditions occur:

If a participant with baseline results of	develops the following elevations:
ALT or AST <1.5x ULN	ALT or AST ≥3x ULN
ALP <1.5x ULN	ALP ≥2x ULN
TBL <1.5x ULN	TBL \geq 2x ULN (except for patients with Gilbert's syndrome)
ALI OF ASI ≥ 1.5 X ULN	ALI of ASI 22x baseline
ALP ≥1.5x ULN	$ALP \ge 2x$ baseline
TBL≥1.5x ULN	TBL \geq 2x baseline (except for patients with Gilbert's syndrome)

If the abnormality persists or worsens, clinical and laboratory monitoring, and evaluation for possible causes of abnormal liver tests should be initiated by the investigator in consultation with the Lilly-designated medical monitor. At a minimum, this evaluation should include physical examination and a thorough medical history, including symptoms, recent illnesses (e.g., heart failure, systemic infection, hypotension, or seizures), recent travel, history of concomitant medications (including over-the-counter), herbal and dietary supplements, history of alcohol drinking and other substance abuse.

Initially, monitoring of symptoms and hepatic biochemical tests should be done at a frequency of 1 to 3 times weekly, based on the participant's clinical condition and hepatic biochemical tests. Subsequently, the frequency of monitoring may be lowered to once every 1 to 2 weeks, if the participant's clinical condition and laboratory results stabilize. Monitoring of ALT, AST, ALP, and TBL should continue until levels normalize or return to approximate baseline levels.

Comprehensive hepatic evaluation

A comprehensive evaluation should be performed to search for possible causes of liver injury if one or more of these conditions occur:

If a participant with baseline results of	develops the following elevations:
ALT or AST <1.5x ULN	ALT or AST \geq 3x ULN with hepatic signs/symptoms*, or
	ALT or AST ≥5x ULN
ALP <1.5x ULN	ALP ≥3x ULN
TBL <1.5x ULN	TBL $\geq 2x$ ULN (except for patients with Gilbert's syndrome)
ALT or AST ≥1.5x ULN	ALT or AST $\geq 2x$ baseline with hepatic signs/symptoms*, or ALT or AST $\geq 3x$ baseline
ALP ≥1.5x ULN	ALP ≥2x baseline

TBL≥1.5x ULN	TBL \geq 1.5x baseline (except for patients with Gilbert's syndrome)

* Hepatic signs/symptoms are severe fatigue, nausea, vomiting, right upper quadrant abdominal pain, fever, rash, and/or eosinophilia >5%.

At a minimum, this evaluation should include physical examination and a thorough medical history, as outlined above, as well as tests for prothrombin time-international normalized ratio; tests for viral hepatitis A, B, C, or E; tests for autoimmune hepatitis; and an abdominal imaging study (e.g., ultrasound or computed tomography scan).

Based on the participant's history and initial results, further testing should be considered in consultation with the Lilly-designated medical monitor, including tests for hepatitis D virus, cytomegalovirus, Epstein-Barr virus, acetaminophen levels, acetaminophen protein adducts, urine toxicology screen, Wilson's disease, blood alcohol levels, urinary ethyl glucuronide, and serum phosphatidylethanol. Based on the circumstances and the investigator's assessment of the participant's clinical condition, the investigator should consider referring the participant for a hepatologist or gastroenterologist consultation, magnetic resonance cholangiopancreatography, endoscopic retrograde cholangiopancreatography, cardiac echocardiogram, or a liver biopsy.

Additional hepatic data collection (hepatic safety CRF) in study participants who have abnormal liver tests during the study

Additional hepatic safety data collection in hepatic safety CRF should be performed in study participants who meet 1 or more of the following 5 conditions:

- 1. Elevation of serum ALT level to ≥5x ULN on 2 or more consecutive blood tests (if baseline ALT <1.5x ULN)
 - ➢ In participants with baseline ALT level ≥1.5x ULN, the threshold is ALT level ≥3x baseline on 2 or more consecutive tests
- 2. Elevation of TBL level to ≥2x ULN (if baseline TBL level <1.5x ULN) (except for cases of known Gilbert's syndrome)
 - ➤ In participants with baseline TBL level ≥1.5x ULN, the threshold should be TBL level ≥2x baseline
- 3. Elevation of serum ALP level to ≥2x ULN on 2 or more consecutive blood tests (if baseline ALP <1.5x ULN)
 - ➢ In participants with baseline ALP level ≥1.5x ULN, the threshold is ALP level ≥2x baseline on 2 or more consecutive blood tests
- 4. Hepatic event considered to be an SAE
- 5. Discontinuation of study drug due to a hepatic event

Note: the interval between the consecutive blood tests should be at least 2 days.

10.5. Appendix 6: Blood Sampling Summary

The following table summarizes the approximate number of venipunctures and blood volumes for all blood sampling (screening, safety laboratories, and bioanalytical assays) during the study.

Purpose	Blood Volume per Sample (mL)	Number of Blood Samples	Total Volume (mL)
Screening chemistry and hematology ^a	3	1	3
Bedside point-of-care glucose monitoring ^b	-	9	0.01
Pharmacokinetics (plasma glucagon)	2	3	6
Pharmacodynamics (plasma glucose)	0.1	5	0.5
Blood discard for cannula patency	1	5	5
Total			14.51
Total for clinical purposes [rounded up to the nearest 10 mL]			20

Protocol I8R-MC-IGBO Sampling Summary for full sampling

a Additional samples may be drawn if needed for safety purposes.

b Applies only to participants for whom a point-of-care blood glucometer will be used, i.e., this is not needed for participants who are using their own continuous glucose monitoring equipment (see Section 8.2.4.1). The volume of each glucose measurement using a point-of-care blood glucometer is estimated at 0.3 to 1.5 μL (0.0003 to 0.0015 mL; ADA 2020).

Term	Definition
AE	adverse event
ALP	alkaline phosphatase
ALT	alanine aminotransferase
AST	aspartate aminotransferase
AUC	area under the concentration-time curve
BG	blood glucose
BGmax	maximum observed BG
CGM	continuous glucose monitoring
complaint	A complaint is any written, electronic, or oral communication that alleges deficiencies related to the identity, quality, purity, durability, reliability, safety or effectiveness, or performance of a drug or drug delivery system.
compliance	Adherence to all study-related, good clinical practice (GCP), and applicable regulatory requirements.
CRF	case report form
CRO	contract research organization
CRP	clinical research physician: Individual responsible for the medical conduct of the study. Responsibilities of the CRP may be performed by a physician, clinical research scientist, global safety physician, or other medical officer.
eCRF	electronic case report form
enroll	The act of assigning a participant to a treatment. Participants who are enrolled in the study are those who have been assigned to a treatment.
enter	Participants entered into a study are those who sign the informed consent form directly or through their legally acceptable representatives.
GCP	good clinical practice
IB	Investigator's Brochure
ICF	informed consent form
ICH	International Council for Harmonisation
IEC	Independent Ethics Committee

2. ABBREVIATIONS

Abbreviations pertain to the Statistical Analysis Plan (SAP) only (not the tables, figures and listings [TFLs]).

AE Adverse event

AUC Area under the concentration versus time curve

BG Blood glucose

BG_{max} Maximum observed blood glucose

CGM Continuous glucose monitoring

C_{max} Maximum observed drug concentration

CRF Case Report Form

CSR Clinical Study Report

ICH International Conference on Harmonisation

MedDRA Medical Dictionary for Regulatory Activities

NG Nasal glucagon

PD Pharmacodynamic

PG Plasma Glucose

PK Pharmacokinetic

SAP Statistical Analysis Plan

SD Standard deviation

SOP Standard Operating Procedure

T1D Type 1 diabetes

TBG_{max} Time of maximum observed blood glucose

TEAE Treatment-emergent adverse event

TFLs Tables, Figures, and Listings

WHO World Health Organization

Labcorp Study: 1001215-8442739 Protocol Reference: I8R-MC-IGBO

3. INTRODUCTION

This SAP has been developed after review of the Clinical Study Protocol (final version dated 19 March 2021).

This SAP describes the planned analysis of the safety, tolerability, pharmacokinetic (PK), and pharmacodynamic (PD) data from this study. A detailed description of the planned TFLs to be presented in the clinical study report (CSR) is provided in the accompanying TFL shell document.

The intent of this document is to provide guidance for the statistical and PK analyses of data. In general, the analyses are based on information from the protocol, unless they have been modified by agreement with Eli Lilly and Company. A limited amount of information concerning this study (e.g., objectives, study design) is given to help the reader's interpretation. For open-label studies, this SAP must be signed off prior to first patient visit for this study. When the SAP and TFL shells are agreed upon and finalized, they will serve as the template for this study's CSR.

This SAP supersedes the statistical considerations identified in the protocol; where considerations are substantially different, they will be so identified. If additional analyses are required to supplement the planned analyses described in this SAP, they may be performed and will be identified in the CSR. Any substantial deviations from this SAP will be agreed upon with Eli Lilly and Company and identified in the CSR. Any minor deviations from the TFLs may not be documented in the CSR.

This SAP is written with consideration of the recommendations outlined in the International Conference on Harmonisation (ICH) E9 Guideline entitled Guidance for Industry: Statistical Principles for Clinical Trials¹ and the ICH E3 Guideline entitled Guidance for Industry: Structure and Content of Clinical Study Reports².

4. STUDY OBJECTIVES

4.1 Primary Objective

The primary objective is to assess the safety and tolerability of a single dose of nasal glucagon (NG) 3 mg in children aged 1 to <4 years with type 1 diabetes (T1D).

4.2 Secondary Objectives

The secondary objectives are:

- To assess the PD of a single dose of 3 mg NG in children aged 1 to <4 years with T1D
- To assess the PK of a single dose of 3 mg NG in children aged 1 to <4 years with T1D.

4.3 Exploratory Objective

The exploratory objective is to assess the efficacy of a single dose of 3 mg NG in children aged 1 to <4 years with T1D.

Labcorp Study: 1001215-8442739

5. STUDY ENDPOINTS

5.1 **Primary Endpoint**

The primary endpoint is the incidence of treatment-emergent adverse events (TEAEs).

5.2 **Secondary Endpoints**

The secondary endpoints are:

- Change from baseline of maximum blood (plasma) glucose
- The following plasma glucose (PG) parameters:
 - o maximum observed blood glucose (BG_{max})
 - o area under the concentration-time curve (AUC)
 - o time of maximum observed blood glucose (TBG_{max})
- Model-estimated population PK parameters

5.3 **Exploratory Endpoint**

The exploratory endpoint is the proportion of patients achieving treatment success defined as an increase of PG ≥20 mg/dL (1.11 mmol/L) from baseline within 30 min postdose

6. STUDY DESIGN

[figure not shown]
Study IGBO is a Phase 1, open-label, multi-center study with a primary objective of assessing safety and tolerability of a single 3 mg dose of NG in pediatric patients aged 1 to <4 years with T1D.

Patients will attend study visits, including screening, in the company of 1 or more parents or legal guardians, and in accordance with local healthcare facility practice.

The study comprises a single cohort, with each patient receiving a single dose of 3 mg NG. At least 9 patients with an approximate maximum of 20 may be enrolled so that 6 evaluable patients complete the study.

For the purposes of this study, a patient completes the study after the conclusion of the second follow-up telephone call on Day 9 (± 3).

A study schema can be seen in Figure 1.

^{*} Predosing-visit telephone call is not required if screening takes place on Day -1.

Figure 1: Study Schema for IGBO

7. TREATMENT

The following is a list of the study treatment that will be used in the TFLs.

Study Treatment Name	Treatment order in TFL	
3 mg nasal glucagon	1	

8. SAMPLE SIZE JUSTIFICATION

At least 9 patients with an approximate maximum of 20 may be enrolled so that 6 evaluable patients complete the study.

Labcorp Study: 1001215-8442739 Protocol Reference: I8R-MC-IGBO

The sample size is customary for Phase 1 studies evaluating safety, tolerability, PD, and PK, and is not powered on the basis of statistical hypothesis testing.

The sample size assumes a 33% dropout rate.

Patients who are enrolled but not administered treatment may be replaced to ensure that enough patients may complete the study. Patients that do not have at least 1 PD postbaseline measure may also be replaced.

9. DEFINITION OF ANALYSIS POPULATIONS

The "Efficacy" population will consist of all patients who received at least one dose of NG, and have baseline and at least 1 postbaseline PG measure within 30 minutes after dose administration. For rescued patients, data after the rescue would be excluded from the analysis.

The "Safety" population will consist of all patients who received at least one dose of NG, whether or not they complete all protocol requirements.

The "Pharmacokinetic" population will consist of all patients who received at least one dose of NG and have evaluable PK data. For rescued patients, data after the rescue would be excluded from the analysis.

The "Pharmacodynamic" population will consist of all patients who received at least one dose of NG and have evaluable PD data. For rescued patients, data after the rescue would be excluded from the analysis.

All protocol deviations that occur during the study will be considered for their severity/impact and will be taken into consideration when patients are assigned to analysis populations.

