Admission to site			х			It is recommended that participants have a natural overnight fast if possible, assuming morning dosing. At a minimum, participants should have no food or beverage intake other than water within 3 hours before dosing.
Verification of hypoglycemia history since screening			Predose			See Section 5.2.1.
Allocation of participant enrollment number			х			Once eligibility is confirmed and participant is ready for dosing.
Baseline glucose measurement			Х			See Section 4.1.4.

Procedure	Screening Visit	Predosing-visit preparation reminder (telephone)	Dosing Visit	Follow-up (telephone)	Second Follow-up (telephone)	Comments
	Day -35 to Day -1	Day -1	Day 1	Day 2	Day 9±3	
If necessary to achieve target glucose level, adjust basal rate or administer a small bolus via insulin pump; or for MDI, infuse a small correction bolus of insulin diluted in normal saline through IV or by SC injection			Predose			At PI's discretion. See Section 4.1.4.
Nasal inspection	Х		Predose, 90 min			Visual nasal inspections. On Day 1, the predose inspection, administration of NG, and postdose inspection (90 min) should all be done by the same person.
Return insulin pump basal rate to pre- study settings			Postdose			For pump users only. If basal rate was adjusted to achieve target blood glucose on the study day, the basal rate must be returned to participant's normal rate prior to discharge.

Procedure	Screening Visit	Predosing-visit preparation reminder (telephone)	Dosing Visit	Follow-up (telephone)	Second Follow-up (telephone)	Comments
	Day -35 to Day -1	Day -1	Day 1	Day 2	Day 9±3	
NG administration			х			Nasal glucagon will be administered only if a participant's baseline glucose level is within target range. See Section 4.1.4.
Sample collection for measurement of plasma glucagon (pharmacokinetics)			10, 30, 60 min			Time points are relative to NG administration.
Bedside glucose safety measurements			Х			Measured using a point-of-care blood glucose testing device: either CGM, if applicable, via IV cannulation, or using an approved BG meter. See Section 8.2.4.1. Blood glucose readings will be taken every 5 to 10 min for the first 30 min after dosing, and then every 20 min up to 90 min. Additional measurements may be taken at investigator's discretion. When a planned bedside safety sample coincides with a PD sample, the PD sample may be used for bedside safety assessment.

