Sample collection for measurement of plasma glucose (pharmacodynamics)			P, 10, 30, 60, 90 min			Measured with study-approved rapid glucose analyzer (Section 8.6). Timings are relative to NG administration.

Procedure	Screening Visit	Predosing-visit preparation reminder (telephone)	Dosing Visit	Follow-up (telephone)	Second Follow-up (telephone)	Comments
	Day -35 to Day -1	Day -1	Day 1	Day 2	Day 9±3	
Meal			Х			Following completion of all study procedures, the participant will be provided a meal including carbohydrates, and the investigator will ensure the participant's plasma glucose is stable prior to discharge.
Discharge from site			Х			Participants may be discharged after 4 hours postdose safety monitoring is complete. If required, a participant may remain in clinic for further observation, at the discretion of the investigator.

Abbreviations: AE = adverse event; BG = blood glucose; CGM = continuous glucose monitoring; IV = intravenous; MDI = multiple daily injection; NG = nasal glucagon; P = predose; PD = pharmacodynamics; PI = principal investigator; SC = subcutaneous.

2. Introduction

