8.3.6.1. Criteria for Considering Rescue Treatment

In general, the investigator may decide to start a glucose infusion if a participant's BG level is declining rapidly, or their symptoms become consistent with progression to clinically significant or severe hypoglycemia.

In addition, specific BG thresholds for considering rescue treatment at baseline and during bedside glucose safety monitoring are as follows:

Baseline criteria for rescue

If a participant's baseline BG level is

- <70 mg/dL, the investigator will determine whether to proceed with dosing or to use rescue treatment.
- <54 mg/dL (clinically significant hypoglycemia [Level 2]), site will halt study drug procedure and use rescue therapy to raise BG level. Such participants' visits may be rescheduled for a subsequent visit.

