9.4.3. Exploratory Endpoint: Efficacy

PG levels will be measured prior to the administration of glucagon, as well as at various time points after administration (SoA, Section 1.3), and may be used to assess efficacy of NG.

Efficacy of NG will be assessed in terms of "treatment success." This is defined as an increase of $PG \ge 20 \text{ mg/dL} (1.11 \text{ mmol/L})$ from baseline within 30 minutes postdose. The proportion of participants achieving treatment success will be calculated.

A Kaplan-Meier curve will be constructed for the time-to-achieve treatment success.

Evaluable efficacy outcome is defined as having baseline and at least 1 postbaseline measure within 30 minutes after dose administration. For rescued participants, data after the rescue would be excluded from the analysis.

The details will be provided in the SAP.

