10.5 Efficacy Assessment

Plasma glucose levels will be measured prior to the administration of glucagon, as well as at various time points after administration and will be used to assess the efficacy of NG.

Efficacy of NG will be assessed in terms of "treatment success", in which treatment success is defined as an increase of PG \geq 20 mg/dL (1.11 mmol/L) from baseline within 30 minutes postdose. The proportion of patients achieving treatment success will be calculated, summarized, and listed. Rescued patients, data after the rescue would be excluded from the analysis, see Section 10.6.2 for further information on rescued patients.

The time to treatment success will be summarized and listed.

A Kaplan-Meier curve will be constructed for the time-to-achieve treatment success.

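### Exploratory treatment success: a child rescued before the 10-minute glucose sample leaves the denominator, and one rescued between 10 and 30 minutes would most naturally be censored in the Kaplan-Meier curve

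*SAP*

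**What the plan says.** Treatment success is a PG rise of at least 20 mg/dL from baseline within 30 minutes of dosing (Protocol 9.4.3; SAP 5.3 and 10.5).

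- **Who is analysed.** For dosed children with a predose value, SAP 9 asks for "at least 1 postbaseline PG measure within 30 minutes after dose administration. For rescued patients, data after the rescue would be excluded". Protocol 9.4.3 agrees: "Evaluable efficacy outcome is defined as having baseline and at least 1 postbaseline measure within 30 minutes after dose administration". Protocol 9.4 limits efficacy analyses to dosed children with such an outcome.
- **When PG is sampled.** The Schedule of Activities (Protocol 1.3) gives "P, 10, 30, 60, 90 min". Only the 10- and 30-minute samples fall in the success window.
- **Rescue.** SAP 10.5 repeats "Rescued patients, data after the rescue would be excluded from the analysis" and refers to SAP 10.6.2. That section says when rescue is used and what is listed. It assigns no efficacy outcome to a rescued child, and it says that bedside glucose readings are not databased.
- **Time to success.** "A Kaplan-Meier curve will be constructed for the time-to-achieve treatment success". SAP 10.5 gives no event, censoring or rescue convention beyond the exclusion of post-rescue data.
- **Sampling after rescue.** Protocol 8.3.6.2 continues the scheduled samples where possible.
- **Replacement.** SAP 8 allows replacement of a child with no postbaseline PD measure.

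**The concern.** Protocol 8.3.6.1 and SAP 10.6.2 link rescue to rapidly declining glucose or to symptoms progressing towards hypoglycemia. A child in that state is less likely than the others to be heading for a 20 mg/dL rise. Removing the child from the denominator, or censoring the child as if still as likely to succeed as those who remain, therefore tends to overstate success.

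Two results that SAP 10.5 asks for on the same children, the proportion and the curve, could also disagree. In a study of this size one child is visible in the percentage. Because the study is open-label, a rule settled after the data are seen would be settled with the outcome known.

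**Working it through.** **The plan's own figure.** Six evaluable children at 33% dropout: 6 / (1 − 0.33) = 8.96, rounded up to 9. This matches the stated minimum enrolment, and the point does not dispute it.

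**Which children are affected.**

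| Rescue, without prior success | Eligible PG within 30 min | Proportion | Kaplan-Meier curve |
|---|---|---|---|
| Before the 10-min sample | None | Leaves the denominator (natural reading) | Not in the population |
| Between 10 and 30 min | 10-min value | Stays, non-success | Most naturally censored at rescue |
| After 30 min | 10 and 30 min | Unaffected | Unaffected within 30 min |

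The second row presumes that the 10-minute sample was obtained. If it was missed, that child drops out as in the first row.

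**How wide the early window is.** The Schedule of Activities says "Blood glucose readings will be taken every 5 to 10 min for the first 30 min after dosing". At 5-minute spacing one scheduled reading (5 min) precedes the 10-minute PG sample. At 10-minute spacing none does, and "When a planned bedside safety sample coincides with a PD sample, the PD sample may be used for bedside safety assessment". Rescue before 10 minutes would therefore rest on one reading, an extra reading, CGM or symptoms.

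**Effect on the proportion, one early rescue (assumed).** Let n children be dosed, including the rescued child, and let the others succeed at rate s. Excluding the child gives s. Counting the child as a non-success gives s(n − 1)/n. The difference is s/n.

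- n = 7 (the planned 6 evaluable plus the rescued child), s = 1: 6/6 = 100% against 6/7 = 85.7%, 14.3 points.
- n = 9, s = 1: 8/8 = 100% against 8/9 = 88.9%, 11.1 points.
- n = 20, s = 1: 19/19 = 100% against 19/20 = 95.0%, 5.0 points.
- With s = 2/3 the differences are (2/3)/7 = 9.5, (2/3)/9 = 7.4 and (2/3)/20 = 3.3 points.

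**Effect on the curve, one rescue at 15 min (assumed).** Let k of n succeed at 10 min (about one third), and let all but one of the remaining n − k − 1 unrescued children succeed at 30 min. Censoring at rescue gives 1 − [(n − k)/n] × [1/(n − k − 1)]. Holding the child as a non-event gives 1 − 2/n, which equals the proportion.

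| n | k | Censored at rescue | Held through 30 min = proportion | Gap |
|---|---|---|---|---|
| 6 | 2 | 1 − (4/6)(1/3) = 77.8% | 4/6 = 66.7% | 11.1 |
| 9 | 3 | 1 − (6/9)(1/5) = 86.7% | 7/9 = 77.8% | 8.9 |
| 20 | 7 | 1 − (13/20)(1/12) = 94.6% | 18/20 = 90.0% | 4.6 |

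In general the gap is (1/n) × (30-min successes)/(n − k − 1). It is zero if none of the remaining children succeeds at 30 min. It reaches its ceiling of 1/n if all do: for n = 6, k = 3, that is 100% against 83.3%.

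**The case against.** The strongest reply is that the documents state a consistent choice: efficacy is assessed in children with an evaluable outcome, and glucose after rescue is not used. Success is defined as a PG rise, so scoring rescue as failure turns it into a composite. It would also count as a failure a child who was rescued pre-emptively and has no postdose PG. The endpoint is exploratory, and Protocol 8.1 says only that efficacy may be assessed. No hypothesis is tested, excluded patients are highlighted in listings (SAP 10.1), and a reader could reclassify one child by hand.

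Most of this stands and keeps the point minor. Excluding post-rescue glucose is sound. The remaining problem is that the stated choice leaves out, or censors, children for a reason related to the outcome.

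Several stronger readings are tempting and are not supported:

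- A reader might infer that every child rescued within 30 minutes drops out. With a 10-minute value, the child stays in and has no qualifying rise in the eligible data.
- A reader might infer that the plan is silent on rescue in the curve. Excluding post-rescue data points towards censoring at rescue, although SAP 10.5 does not say so. The separate TFL shells, which are not available here, may add a convention.
- A reader might put the effect on the proportion at 17 points, from 6 dosed and one early rescue (5/5 against 5/6). That leaves five evaluable children, while the plan seeks six and allows replacement.
- A reader might think early rescue likely because, below 70 mg/dL, "the investigator will determine whether to proceed with dosing or to use rescue treatment" (Protocol 8.3.6.1, also 2.3.1.1). The Schedule of Activities instead permits dosing only within the target range, which is 70 to 140 mg/dL. These passages must be reconciled, and this point does not rely on that route.
- A literal reader might keep the early-rescued child in the population because samples continue after rescue. The child would then have no usable value, and still no rule would classify the outcome.

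**Conclusion.** The point holds as a minor one, confined to the exploratory success endpoint. A dosed child rescued before the 10-minute sample leaves the denominator on the natural reading. A child rescued between 10 and 30 minutes without success is correctly a non-success in the proportion, but would most naturally be censored in the curve. Both tend to favour the product.

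For one assumed early rescue with all others succeeding, the overstatement is about 14 points at 7 dosed, 11 at 9 and 5 at 20. For one assumed later rescue, the curve exceeds the proportion by about 5 to 11 points under the response pattern used above. The documents give no rescue rate, the early window is narrow, and hypoglycemia is not induced in this study. The likeliest effect is therefore none. The Safety population keeps every dosed child, so the primary endpoint is untouched.

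**What to change.** Add to SAP 9 and 10.5, and record in SAP 12 as a change from the protocol's evaluable-outcome definition:

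- Keep in the Efficacy population, as a non-success, every dosed child with a baseline PG who is rescued within 30 minutes before success. This applies whether or not a PG sample precedes the rescue, and even if the child is replaced.
- In the Kaplan-Meier curve, hold such children as non-events through 30 minutes instead of censoring them at rescue.
- Continue to exclude post-rescue glucose from the PD summaries.
- Report how many children were classified this way.

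The cost is two or three sentences plus one line in SAP 12, best settled before efficacy data are seen. Protocol 9.4 requires an amendment only for a change to a principal feature, so this can be made in the SAP. Care and sampling do not change. The downside is that the proportion may look slightly less favourable, and a pre-emptively rescued child is scored as a non-success although the response without rescue was never observed. Reporting the count makes that visible.
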